11.1. Sample Size

This is a single-arm study with its primary efficacy endpoint being ORR. This study includes patients refractory to sorafenib and patients not treated with sorafenib. The sample size of these two groups is calculated based on the hypothetical conditions below.

Subjects refractory to sorafenib

Assuming that the treatment efficacy is less than 10% for standard treatment and is 25% for PD-1 plus apatinib, and a two-sided $\alpha = 0.05$, then a total of 64 patients are required to provide a power of 90%. If the dropout rate is 20%, 80 subjects should be enrolled.

The number of patients who failed sorafenib can be increased to 120 at late stages in the trial to better determine the efficacy and safety of the investigational drug in this population.

Subjects not treated with sorafenib

Assuming that the treatment efficacy is less than 15% for standard treatment and is 30% for SHR-1210 plus apatinib, and a two-sided $\alpha = 0.05$, then a total of 56 subjects are required so that the half-width of the 95% confidence interval of overall ORR does not exceed 12%.

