11.5.3. Efficacy Endpoint Analysis

Point estimates and 95% CI will be used for efficacy endpoints such as objective response rate (ORR) and disease control rate (DCR). The confidence intervals are estimated using the Clopper-Pearson method.

PFS, DOR, OS, and 9-month and 12-month survival rates, as well as their respective 95% CIs will be estimated using the Kaplan-Meier method. The two-sided 95% CI of the median PFS, DOR, and OS will be estimated using Brookmeyer-Crowley method. For the two-sided 95% CI of 9-month and 12-month overall survival rates, the 95% CI after log-log transformation is calculated using the normal approximation method followed by inverse transformation. TTR is described using mean, standard deviation, median, maximum, and minimum.

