#### **Patients who have not received systemic first-line treatment**

Assuming that the standard treatment efficacy is no greater than 15%, that the efficacy of SHR-1210 in combination with apatinib mesylate is 30%, and that  $\alpha = 0.05$  (two-sided), the enrollment of 56 patients can ensure that the half width of 95% confidence interval (CI) of overall ORR be no more than 12%.

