### **3. STATISTICAL HYPOTHESIS AND DECISION RULE**

Statistical hypothesis for patients with systemic first-line treatment failure is as follows:

Null hypothesis:  $ORR = 10\%$

Alternative hypothesis:  $ORR \neq 10\%$

If the lower limit of 95% CI of ORR is greater than 10%, PD-1 antibody SHR-1210 in combination with apatinib can be considered effective in the treatment of advanced hepatocellular carcinoma with systemic first-line treatment failure.

The decision rule for patients who have not experienced systemic first-line treatment failure is as follows:

If the lower limit of 95% CI of ORR is greater than 15%, it suggests that PD-1 antibody SHR-1210 in combination with apatinib is effective in the treatment of advanced hepatocellular carcinoma without systemic first-line treatment failure.

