### **5.4. Efficacy Analysis**

ORR and DCR are analyzed based on FAS and ES. Other efficacy analyses are performed based on FAS.

All efficacy analyses are performed according to the following populations (population with systemic first-line treatment, population without systemic first-line treatment, and total population).

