#### **5.4.1.1. Objective response rate (ORR)**

See Section 4.1.1 for the definition of objective response rate.

For the primary endpoint ORR, the proportion of all enrolled subjects whose best overall response (BOR) is assessed as complete response (CR) or partial response (PR) as per RECIST v1.1 is descriptively summarized. The ORR is calculated along with the corresponding two-sided 95% CI calculated using the Clopper-Pearson method. Data of best overall response evaluation will be listed and summarized.

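### The 56 patients without prior sorafenib were sized with the normal-approximation interval; the Clopper-Pearson interval the plan will report has a half-width of about 12.5 to 12.7 points, not at most 12.

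*Protocol*

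**What the plan says.** The protocol sizes two cohorts separately. For patients not treated with sorafenib, Protocol 11.1 assumes a standard-treatment rate below 15% and an ORR that "is 30% for SHR-1210 plus apatinib", with two-sided alpha 0.05. It concludes that "a total of 56 subjects are required so that the half-width of the 95% confidence interval of overall ORR does not exceed 12" per cent. The synopsis repeats this. SAP 2.3 is firmer: "the enrollment of 56 patients can ensure that the half width of 95% confidence interval (CI) of overall ORR be no more than 12" per cent. Neither document names the interval behind this calculation.

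Both name the interval to be reported. Protocol 11.5.3, on ORR and DCR, says: "The confidence intervals are estimated using the Clopper-Pearson method". SAP 5.4.1.1 plans "the corresponding two-sided 95% CI calculated using the Clopper-Pearson method", and SAP 5.4 applies the efficacy analyses to the "population with systemic first-line treatment, population without systemic first-line treatment, and total population".

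SAP 3 adds a rule for this cohort that Protocol 11.2 does not contain. It begins "If the lower limit of 95% CI of ORR is greater than 15" per cent, and meeting it is taken to suggest efficacy. No power is given for it.

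**The concern.** A precision statement describes the interval that readers will eventually see. Here that interval is Clopper-Pearson, which at this sample size and response rate is wider than the normal approximation. If 56 was derived from the narrower interval, the 12% limit does not describe the planned analysis. This sentence is the only stated justification for the size of the cohort, in a trial whose primary endpoint is ORR.

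The preceding paragraph of the same section does agree with the planned interval. For the refractory cohort, a lower Clopper-Pearson limit above 10% needs 12/64 (lower limit 10.08%; 11/64 gives 8.90%), and the exact power at 25% is 90.7%, in line with the stated 90%. The two cohorts are therefore justified on different footings, and the text does not say so.

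**Working it through.** **Inputs.** n = 56, assumed ORR p = 0.30, target half-width d = 0.12 and two-sided 95% confidence (Protocol 11.1, SAP 2.3). The reported interval is Clopper-Pearson (Protocol 11.5.3, SAP 5.4.1.1). The 15% rule is from SAP 3.

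**1. The plan's own figure.** The Wald formula is n = z² p(1 − p)/d² = 1.96² × 0.30 × 0.70 / 0.12² = 56.02. At n = 56 the half-width is 1.96 × √(0.21/56) = 12.002%. The stated 56 is reproduced, and the excess over 12% is only rounding.

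**2. The planned interval at n = 56.** For x responders the lower limit is the 0.025 quantile of Beta(x, n − x + 1), and the upper limit is the 0.975 quantile of Beta(x + 1, n − x). The half-width is half the distance between them.

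| Responders | ORR | 95% CI | Half-width |
|---|---|---|---|
| 14 | 25.0% | 14.4% to 38.4% | 11.99% |
| 15 | 26.8% | 15.8% to 40.3% | 12.23% |
| 16 | 28.6% | 17.3% to 42.2% | 12.46% |
| 17 | 30.4% | 18.8% to 44.1% | 12.66% |

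An ORR of exactly 30% would be 16.8 responders. Interpolating there gives 12.62%.

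**3. Over sampling variation.** Weighting the half-widths by Binomial(56, 0.30) gives an expected half-width of 12.50%. The half-width is at most 12% when x ≤ 14, with probability 25.5%. It is also met from 42 responders upward, which has negligible probability at a true 30%.

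**4. Size of the gap.** The half-width exceeds the target by 12.50 − 12.00 = 0.50 points on average and by 12.66 − 12.00 = 0.66 points at 17/56. The n that would meet 12% with Clopper-Pearson depends on the criterion:
- expected half-width: about 61
- interpolated at exactly 30%: 62
- nearest whole count: 63 (19/63 gives 11.90%; 19/62 gives 12.04%)
- at least an 80% chance of meeting 12%: about 67

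On the first three criteria the gap is 5 to 7 patients.

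**5. Which ORR is meant.** Across all 136 patients, 41/136 (30.1%) gives a half-width of 8.0%. Only the cohort reading reproduces 56.

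**6. The 15% rule.** The smallest x with a lower limit above 15%, and its exact power at a true 30%:

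| Patients analysed | Responders needed | Power at 30% |
|---|---|---|
| 53 | 14 | 76% |
| 54 | 15 | 69% |
| 56 | 15 | 74.5% |
| 58 | 15 | 80% |
| 59 | 16 | 73% |

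At n = 56, 14 responders give a lower limit of 14.4% and fail; 15 give 15.8% and pass.

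**The case against.** The strongest reply is that nothing was miscalculated. The normal approximation is a standard planning formula, it gives 56, and neither document says that Clopper-Pearson was used for planning. Wilson (11.68%) and Agresti-Coull (11.75%) intervals would meet 12% at n = 56. This stands: the fault is a mismatch between the planning and analysis methods. A reader who infers an arithmetic error goes further than the documents allow.

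A second reply is that a precision statement is normally conditional on the assumed rate and does not promise anything about every sample. By the 25% test even the Wald half-width meets 12% only 47% of the time. This also stands, so the probability should not carry the point alone. But the claim fails on the conditional reading too, at 12.62% for an ORR of 30%. Only the SAP's verb *ensure* invites the probabilistic reading.

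Third, *overall ORR* might be taken to mean the total population. The sentence sits under the cohort's own heading, and at n = 136 the limit would hold easily, so this is loose wording and no more.

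Fourth, a reader might infer that the 15% rule carries the 90% power of the other cohort. Neither document says so. Both attach 90% to the sorafenib-refractory (SAP: first-line-failure) cohort only and offer this one precision alone. What can be said is that the rule's power is not stated.

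Finally, the actual interval will be reported whatever the planning sentence says, so readers of the results will see the true precision. That is a fair reason to treat the matter as wording.

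**Conclusion.** The point holds in a limited form. With the interval both documents specify, 56 patients give a half-width of about 12.5 to 12.7 points at an ORR near 30%. The statements that it does not exceed 12%, and that 56 can ensure this, are not true of the planned analysis. The shortfall is 0.5 to 0.7 points. It does not affect the hypothesis test in the refractory cohort or bias any estimate, and it does not show that the cohort is too small for a precision objective.

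This rests on a true ORR of 30%, exactly 56 patients in the full analysis set, and the cohort being analysed on its own as SAP 5.4 provides. The SAP plans about 56, so the figures will shift slightly with the number treated. The 15% rule shifts more: its power is not monotone in n and lies between about 69% and 80% for 53 to 59 patients.

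**What to change.** Keep 56. In Protocol 11.1, the synopsis and SAP 2.3, replace the precision sentence with:

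> With 56 patients and an ORR of about 30%, the expected Clopper-Pearson 95% CI half-width for the ORR in this cohort is about 12.5 to 12.7 percentage points (for example 17/56: 18.8% to 44.1%).

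Drop *ensure* from the SAP. Replace *overall ORR* with the cohort name each document uses: patients not treated with sorafenib in the protocol, and patients who have not received systemic first-line treatment in the SAP. Naming the normal approximation as the planning method would explain 56, but would not make the 12% limit true of the reported interval.

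In SAP 3, add that with exactly 56 patients in the full analysis set the 15% rule needs at least 15 responders and has about 75% exact power at a true ORR of 30%. Add that both change with the actual n: 14 responders at 53 patients, 15 at 54 to 58 and 16 at 59, with power of about 69% to 80%.

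The cost is wording only. No patients, endpoints or analyses change, and the stated precision becomes about half a point less favourable.

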11.2. Statistical Hypothesis and Discriminatory Rules

The hypothesis for population refractory to sorafenib are as follows:

Null hypothesis: $\text{ORR} = 10\%$

Alternative hypothesis: $\text{ORR} \neq 10\%$

Efficacy is established for PD-1 antibody SHR-1210 plus apatinib in patients with advanced HCC refractory to sorafenib if the lower limit of the 95% CI of ORR is greater than 10%.

11.3. Statistical Analysis Plan

Statistical analysis for data collected in this study will be documented in the Statistical Analysis Plan (SAP) which will be finalized and filed by the sponsor. If there are any changes to the study protocol that are deemed significant by the sponsor or principal investigator to the statistical analysis, the SAP will be revised accordingly to conform to the study protocol. Relevant content in this SAP that is relevant to the protocol may be revised. However, if revised content involves the main and/or key factors of the protocol, such as the definition of primary endpoints or their analysis, such content in the protocol will be revised.

11.4. Analysis Population

- Full analysis set: including all enrolled subjects who have received at least one study dose.
- Safety analysis set: including all enrolled patients who have received at least one dose of the investigational drug and have safety data after the dose. This dataset is used for safety analysis.

11.5. Statistical Methods

11.5.1. Basic Methods

Trial results are mainly analyzed using descriptive statistics. Numerical data will be summarized in means, standard deviations, medians, maximums, and minimums. Categorical data will be summarized in frequencies (proportions), percentages, and confidence intervals.

Statistical analysis will be performed using the SAS 9.4 or above.

11.5.2. Baseline characteristics

The mean, standard deviation, median, maximum, and minimum of quantitative data such as age, height, and weight are calculated, and the frequency and percentage of qualitative data such as gender and ECOG PS are listed.

11.5.3. Efficacy Endpoint Analysis

Point estimates and 95% CI will be used for efficacy endpoints such as objective response rate (ORR) and disease control rate (DCR). The confidence intervals are estimated using the Clopper-Pearson method.

PFS, DOR, OS, and 9-month and 12-month survival rates, as well as their respective 95% CIs will be estimated using the Kaplan-Meier method. The two-sided 95% CI of the median PFS, DOR, and OS will be estimated using Brookmeyer-Crowley method. For the two-sided 95% CI of 9-month and 12-month overall survival rates, the 95% CI after log-log transformation is calculated using the normal approximation method followed by inverse transformation. TTR is described using mean, standard deviation, median, maximum, and minimum.

11.5.4. Safety Analysis

Descriptive statistical analysis is primarily used to analyze the AEs, CTCAE Grade ≥ 3 , serious adverse events and adverse reactions, \geq Grade 3 adverse reactions, and AEs leading to dose modification in each population (the adverse reactions are defined as adverse events that are "definitely related, possibly related, and not assessable" to the investigational drug). Laboratory test results describe the baseline and the worse on-treatment value.

Besides, irAEs, including immune-related pneumonitis, immune-related enteritis, immune-related thyroid dysfunction, immune-related nephritis and renal failure, and immune-related hypophysitis, will be categorized and summarized using above summary analysis of AEs.

11.5.5. Exploratory Analysis

Serum HBsAg and alpha-fetoprotein (AFP) levels are summarized descriptively;

SHR-1210-related biomarkers, such as PD-L1 in tumor tissue or TMB in tumor tissue and plasma will be summarized using descriptive statistics.

Acyl-CoA at baseline: The relationship between the expression levels of SOAT1, NPC1, and TGF- β and treatment response will also be summarized using descriptive statistics.

The results of the exploratory biomarker study will be reported separately (except for the results of descriptive statistical analysis) and will not be included in the clinical study report.

The results from the exploratory biomarker study may be combined and analyzed with biomarker data from other studies of the investigational drug to formulate a hypothesis which will be further validated in future studies.

12. DATA MANAGEMENT METHOD

12.1. Data Recording

The investigator must retain all study records and source documents preferably as long as possible, up to the maximum time required by applicable regulations and guidelines, or SOP of the study site, or as specified by Hengrui, whichever is longest. The investigator must first contact Hengrui prior to the destruction of any study-related records.

Hengrui will notify the investigator when these study records are no longer needed.

If the investigator withdraws from the study (e.g., change of positions, retirement), the records should be transferred to designated personnel recognized by both parties (such as another investigator or IRB). Hengrui must be notified in writing for these types of transfers.

12.1.1. Documentation of the Original Medical Records

Original medical records should be retained in their entirety as the source documents.

The investigator is responsible for filling out and keeping the original medical records. Medical records should be neat and legible so the sponsor's monitor can verify data with the eCRF during each inspection.

12.1.2. eCRF Entry

Clinical trial data are collected using the HRTAU EDC system.

Each staff that is authorized to sign the eCRF must meet Hengrui's training requirements and must only log in to the electronic data capture tool with the individual user account provided by Hengrui. The user account shall not be shared with others and shall not be assigned to another staff.

Entry: The data in the eCRF are from and should be consistent with the source documents, such as the original medical records and laboratory test reports. Any observations or test results in the trial should be entered in the eCRF in a timely, accurate, complete, clear, normative and verifiable manner. Data should not be changed arbitrarily. All items in the CRF should be filled out, with no blank or omissions.

Modifications: The system instructions must be followed when correcting the eCRF data as needed, and the reason for data correction must be recorded.

Laboratory examinations: The investigator should conduct all examinations as well as collect, input and report subject information and data according to the follow-up time window. As a source document, the laboratory test report must be complete and the results should be documented in the eCRF in a timely manner.

In addition, other source data include original copies of data recorded or generated by automated instruments, photographic negative, X-ray, CT or MRI, ECG records, and subject daily logs. These documents must at least indicate the subject number and date of the procedure performed. If possible, the medical review of these records should be documented, and signed and dated by the investigator. The information from these source documents must be entered into the eCRF in a timely manner.

12.1.3. eCRF Review

The investigator must complete, review, and submit the eCRF within 10 working days after the end of each subject's treatment course. The investigator should promptly respond to queries raised by the monitor, data manager, and medical reviewer. After data cleaning is completed, the investigator will sign the completed eCRF for verification.

12.2. Data Monitoring and Auditing

The authorized representatives (monitors, auditors, etc.) of Hengrui must be allowed to regularly visit all the study sites to evaluate the quality of data and whether the study is complete and reliable. These representatives will perform an on-site review of the study records by directly comparing these records with the source documents, discuss the implementation of the study with the investigator, and confirm whether the study facilities still meet the requirements.

To confirm that the study protocol is adhered to; the records on CRF is correct, and complete and consistent with the original medical records and laboratory test results, and whether there are errors or omissions in the data. The monitor must check the content in eCRF against the source documents one by one, ensuring that the data in eCRF are consistent with the original source. This process is also known as source data verification (SDV).

In addition, inspectors from regulatory departments may also evaluate the study. These personnel must also be allowed to review the eCRF, source documents, and other study documents, and to inspect the study facilities. Audit reports must be kept confidential. If the regulatory department plans to conduct an inspection, the investigator must immediately notify Hengrui and promptly forward the inspection report.

12.3. Data Management

12.3.1. EDC Database Establishment

The data manager will establish a study data collection system and database according to the study protocol, which will be available for online usage before the first subject is enrolled. Before use, all EDC users should receive adequate training and get the corresponding account to log into the system.

12.3.2. Data Entry and Verification

After the investigator completes and submits eCRF, the monitor, data manager, and medical reviewer should review the data. Questions during the review are submitted to the investigator in the form of queries. After data cleaning is completed, the investigator should sign the completed eCRF for verification.

12.3.3. Database Locking

After SDV is completed by the CRA, the study director, sponsor, statistician, and data administrator must jointly perform the final quality control of all data in the database, summarize all protocol deviations and violations, and hold the data verification meeting to determine the analysis dataset to which each subject belongs (including FAS, PPS, and SS), the judgment of missing values, and the handling of outliers. The database will be locked after quality requirements have been met. The data manager will export the data to the statistics department for data analysis.

12.3.4. Data Archiving

After the study is completed, subject's eCRFs in PDF format must be generated from the EDC system and kept in CD-ROMs. These CD-ROMs will be archived by the sponsor and various institutions for auditing and/or inspection.

All materials should be preserved and managed in accordance with GCP requirements, and necessary documents of clinical trials shall be preserved until 2 years after the investigational drug is approved for marketing or 5 years after the clinical trial is terminated.

13. SOURCE DATA AND DOCUMENTS

According to ICH E6, relevant regulations, and requirements for subject's personal information protection of the study sites, each study site must properly keep all the treatment and scientific records related to this study. As a part of the study that Jiangsu Hengrui Pharmaceuticals Co., Ltd. sponsors or participates in, each study site must allow the authorized representative of Jiangsu Hengrui Pharmaceuticals Co., Ltd. and regulatory authorities to inspect the clinical records (which may be copied if permissible by law) for quality review, audit, and evaluations of safety, study progress, and data validity.

The source data are the whole information that is required to reconstruct and evaluate the clinical study and the original records of clinical findings, observations, and other activities. These source documents and data records include but are not limited to: hospital record, laboratory records, memos, patient diary cards, pharmacy dispensing records, recordings of advisory meetings, recorded data from automated devices, copies or transcripts that are verified to be accurate and intact, microfiche, photograph negatives, microfilms or magnetic disks, X-ray films, and subject's documents and records that are kept in the pharmacies, laboratories, and medical technology departments that are involved in this study.

